### **2.2 Secondary Objectives**

- To describe the change in other patient reported outcomes (SF-36 domain scales, EQ-5D-3L index, WPAI total lost productivity) at weeks 12 and 24 after the initiation of adalimumab, in those patients continuing on adalimumab (responder

population). These changes will be summarized as the means and 95% confidence intervals and will be tested with paired t-tests.

- To describe the change in patient satisfaction questions at weeks 12 and 24 after the initiation of adalimumab, in those patients continuing on adalimumab (responder population). These changes will be summarized as number and percentage of each response and compared with Wilcoxon signed rank test. Satisfaction will also be dichotomized and analyzed over time with Cochran-Armitage test for trends.
- To summarize the number and percent of patients achieving a clinically meaningful improvement on the HAQ DI, as defined by a -0.22 point improvement or greater, at weeks 12 and 24 after the initiation of adalimumab, in those patients continuing on adalimumab (responder population).

### 2.3 Additional Secondary Objectives

- To describe the change in HAQ DI score at 24 weeks after the initiation of adalimumab, in those patients continuing on adalimumab (responder population), compared with those patients not continuing on adalimumab (non-responders). The mean changes in these two groups will be compared using an independent t-test.
- Patient's impression of change in RA at weeks 12 and 24 after the initiation of adalimumab, in those patients continuing on adalimumab (as observed population). Each response will be summarized as number and percentage.
- To summarize the healthcare resource utilization using number and percentage within each category (number of consultations, number of procedures received, number of surgeries, number of hospitalizations and length of stay, number and type of concomitant medications)
- To analyze the associations between disease severity and PROs (HAQ DI, SF-36 domain scales, EQ-5D-3L index, WPAI total lost productivity)
- To analyze the associations between change in disease severity and change in PROs (HAQ DI, SF-36 domain scales, EQ-5D-3L index, WPAI total lost productivity)

## 2.4 Exploratory Objectives

- To explore the potential modifying effects of baseline measures on the changes in primary and secondary efficacy outcomes (i.e. PROs). These measures will include age, gender, baseline severity, and other diagnoses/co-morbidities.

## 3. STUDY DESIGN

### 3.1 Overview of Study Design

This study is designed as a prospective, observational study to assess the effect of adalimumab on health-related QoL and work productivity in patients with RA in China, South Korea, and Taiwan in clinical practice.

RA patients will be recruited from within the clinical settings of each rheumatologist participating in the study. Approximately 243 patients diagnosed with RA that meet the inclusion and exclusion criteria will be enrolled at approximately 26 sites in China, South Korea and Taiwan.

To assess health and disability outcomes, the HAQ DI will be assessed at baseline, Week 12 and Week 24 after treatment initiation with adalimumab. In addition, other PROs of work activity and well-being, including the WPAI, EQ-5D-3L, and SF-36, will also be assessed.

The patients identified by the recruiting investigators (specialty dependent on country/region; e.g. rheumatologist, internists, general practitioners, etc.) based on the study selection criteria will complete a set of patient questionnaires on QoL, functioning, work productivity, treatment satisfaction, impression of change and HCRU. Data will be captured at baseline (D0), Week 12 and Week 24.

The HCRU will also be collected. This includes surgical procedures, hospitalizations, bed days in hospital, physician consultations etc. Costs will be assigned based on the HCRU using standardized costs for each participating countries.

### 3.2 Study Population

Approximately 100 patients diagnosed with RA will be recruited per country from totally 26 sites. All eligible patients within the enrollment period will be included; inclusion and exclusion criteria for the population are as below.

### 3.2.1 ***Inclusion Criteria***

Patients meeting all of the following inclusion criteria at baseline will be included:

- Subject has a diagnosis of RA as defined by the 1987 revised ACR classification criteria and/or the ACR/ the European League against Rheumatism (EULAR) 2010 classification criteria (any duration since diagnosis)
- Male or female subjects  $\geq 18$  years of age (local definition according to adalimumab label) who is in compliance with eligibility for adalimumab based on the local label
- Patients with moderate to severe RA defined as DAS28 (ESR) or DAS28 (CRP) $>3.2$
- Biologically treatment naïve and initiated adalimumab at baseline visit
- Availability of clinical data of the previous 12 weeks prior to baseline
- Ability to self-complete patient questionnaires
- Subject must be able and willing to provide written informed consent and comply with the requirements of this study protocol

### 3.2.2 ***Exclusion Criteria***

Patients meeting any of the following exclusion criteria at baseline will be excluded:

- Patients who are pregnant or breast feeding at enrolment or wish to become pregnant in the next 24 weeks
- Participation in any RA-related clinical trial at the time of enrolment, at baseline or at any point during the past 24 weeks prior to baseline
- Patients, who in the clinician's view, may not be able to accurately report their QoL or prior resource utilization
- Patients, who in the clinician's view, may not be able to adhere to adalimumab therapy over 24 weeks

## 3.3 **Data Sources/Data Collection Process**

### 3.3.1 ***Data Sources***

The data sources of this non-interventional observational study are Case Report Forms (CRFs) and patient questionnaires. Collection of data includes but not limited to subject demographics, clinical history, comorbidities, spontaneous adverse events, and concomitant medications. The following questionnaires will be utilized to collect data directly from participating subjects:

- HAQ DI
- SF-36
- EQ-5D-3L
- WPAI
- Patient Global Impression of Change (PGIC)
- Patient Treatment Satisfaction Questions

- HCRU

### **3.3.2 Data Collection**

IMS will coordinate data collection with each site. At study initiation (Baseline, D0), patients will be asked to provide their written informed consent. The patient then will complete the study questionnaires in paper form. At all follow up visits (week 12 and 24), the patient will complete the study questionnaires while waiting for their appointment at their clinic, approximately 30 minutes before they visit their physicians. It is important that they complete the questionnaires prior to speaking with their clinician during the visit, as the clinician feedback might impact patient perceptions measured by the PRO instruments. There will be a study coordinator or study nurse at each site to monitor the process. The study coordinator/nurse will hand the study questionnaires directly to the patient and collect the questionnaires once they are completed. Physicians will not see the contents patients entered.

Patients must complete the survey by themselves without help from anyone. However, for patients who physically have difficulty filling out the questionnaires, help is allowed as long as there are no suggestions or discussion from the helpers. The study coordinator/nurse will check to ensure all the forms are filled in correctly.

In addition, physicians will also be asked to complete a clinical CRF in paper form based on the patient's medical records at baseline, 12 weeks, and 24 weeks. The CRF completed by physicians will be returned to the study coordinator/nurse at each site as well.

All data filled in by the patient and physician will be collected by the study coordinator/nurse at each site and returned directly to IMS. The data collection time is expected to be 10-13 months.

All patient and clinician data will be handled preserving confidentiality.

### **3.3.3 Ethics and Quality**

Prior to any study-related data being collected, informed consent form will be reviewed, signed and dated by the patient and the person who administered the informed consent. A copy of the signed informed consent will be given to the patient and the original will be placed in the patient's medical record.

### **3.3.4      *Quality Assurance***

Prior to the initiation of the study, physician and site personnel will be trained on the study. Training will include a detailed discussion of the protocol, performance of study procedures, and completion of the CRFs and paper questionnaires.

All sites will be monitored during the course of study participation. One hundred percent (100%) source document review for safety will be performed.

All clinical data will be documented via the CRF. Study coordinators at each site will check the paper CRFs completed by the physicians and questionnaires completed by patients (e.g., all questions were answered). Data entry will be conducted by IMS. After entry of the data, computer logic checks will be run to check for inconsistent data. Any necessary corrections will be made to the database and documented via addenda, queries, and source data clarification forms.

Steps to be taken to ensure the accuracy and reliability of data include the selection of qualified investigators and appropriate study centers; review of protocol procedures with the investigator and associated personnel before the study and periodic monitoring visits by the sponsor. Written instructions will be provided for administration and collection of study questionnaires.

Guidelines for CRF completion will be provided and reviewed with study personnel before the start of the study. The sponsor will review CRFs and patient questionnaires for accuracy and completeness after transmission to the sponsor; any discrepancies will be resolved with the investigator or designee, as appropriate. After upload of the data into the clinical study database they will be verified for accuracy and consistency with the data sources.

## **3.4      *Data Management and Storage Process***

### **3.4.1      *Data Management***

Data management and data quality check will be performed to remove errors and inconsistencies in order to assure the appropriateness of the study data set to assess the study objectives. Data entry screens will be developed and tested prior to initiating data collection to reduce data entry errors. If required, IMS will provide AbbVie with data for analysis.

Each site coordinator will be instructed to answer patients' queries which may arise in relation to the questionnaires and check the patients' input to make sure all questions are answered.

### **3.4.2 Storage Process**

Following data quality checks, each dataset will be converted to SAS and merged for analysis. All information included in the CRF and the patients' questionnaires will be checked in order to detect possible queries to solve and will be extracted to a specifically designed database, where it will be validated by IMS personnel to ensure its quality. Finally, data analysis will be conducted and final results reported.

The databases will be stored in IMS data servers. Data servers are submitted to daily backups in order to increase the security on all data managed in the collection process.

All paper based questionnaires will be stored in a secured, locked area for a period of 7 years, after which all data will be shred using an agency specialized in disposal of confidential documents.

### **3.5 Definitions of Study Variables**

The key variables of interest in this study are demographic and clinical characteristics, patient-reported health and disability outcomes, and healthcare resource utilizations for each country. Most variables will be measured at baseline (i.e. index), and at weeks 12 and 24 after the initiation of Adalimumab; healthcare resource utilization will be summarized over the 6 month post-index period.

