9.7.6 Additional Secondary Endpoint Analysis

Additional efficacy analysis includes:

- Change in HAQ DI score at 24 weeks after the initiation of adalimumab, in those patients continuing on adalimumab, compared with those patients not continuing on adalimumab. The mean changes in these two groups will be compared using an independent t-test.
- Healthcare resource utilization will be described using number and percentage within each category (number of consultations, number of procedures received, number of surgeries, number of hospitalizations and length of stay, number of concomitant medications)
- Associations between disease severity and PROs
- Associations between change in disease severity and change in PROs

Exploratory endpoint

Change in patient satisfaction questions at weeks 12 and 24 after the initiation of adalimumab (observed population). These changes will be summarized as number and percentage of each response and compared with Kruskal-Wallis test. Satisfaction will also be dichotomized and analyzed over time with Cochrane-Armitage test for trends.

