17.0 Discontinuation or Drop-out

Patients' participation in the study is completely voluntary, and they are allowed to withdraw or discontinue from the study. The following three situations will be counted as study drop-out:

- 1) Patient is switched off Adalimumab
- 2) Patient is not willing to continue participation in the study
- 3) Patient disappears and cannot be contacted anymore

For the first two situations, the Early Termination Form (Appendix K) will be provided for the patients and their physicians to fill in.

Patients not completing questionnaires will not be classified as drop-out. For example, if a patient missed Week 12 questionnaires for some reason, he/she can still fill in Week 24 questionnaires.

Once a subject is dropped out from the study, no further information for that subject will be collected. However, the reason for drop-out will be collected and, if the reason for treatment discontinuation is due to an adverse event, the event will be reported as follows :

- SAE : reported to Abbvie within 24 hours of physician awareness

- Non-serious AE : reported to Abbvie within 24 hours of PMOS physician awareness.

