**16. Please check your household income****Mainland China:**

- ₁ Below RMB 8,000
- ₂ RMB 8,000-11,999
- ₃ RMB 12,000-14,999
- ₄ RMB 15,000-19,999
- ₅ RMB 20,000-29,999
- ₆ RMB 30,000 and above
- ₀ Prefer not to tell

Taiwan:

- ₁ Less than NT\$250,000
- ₂ NT\$250,000 – 649,999
- ₃ NT\$650,000 – NT\$1199,999
- ₄ NT\$1,200,000 – NT\$1,799,999
- ₅ NT\$1,800,000 – NT\$2,499,999
- ₆ More than NT\$2,500,000
- ₀ Prefer not to tell

Korea:

- ₁ 0 – 999,999 KRW
- ₂ 1,000,000 – 1,999,999 KRW
- ₃ 2,000,000 – 2,999,999 KRW
- ₄ 3,000,000 – 3,499,999 KRW
- ₅ 3,500,000 – 3,999,999 KRW
- ₆ 4,000,000 – 4,499,999 KRW
- ₇ 4,500,000 – 5,499,999 KRW
- ₈ 5,500,000 – 6,499,999 KRW
- ₉ 6,500,000 – 9,999,999 KRW
- ₁₀ 10,000,000 + KRW
- ₀ Prefer not to tell

1023259 Real-World Impact of RA

		-	
Site number		Participant ID	

Thank you for completing the Healthcare Resource Utilization Questionnaire.
Please return this form to the IMS representative.

Follow-up:

1023259 Real-World Impact of RA

Site number	-	Participant ID

Healthcare Resource Utilization &
Demographic Questionnaire
(Follow-up)

Patient ID	

	-	 Site #	 Participant #	

		-	 Site #	 Participant #	
	-	 Site #	 Participant #			
Today's date	

 Day	/	 Month	/	 Year	

	 Day	/	 Month	/	 Year
 Day	/	 Month	/	 Year		

<Request on entering>

1. Please use ballpoint pen.
2. On selecting the item, please check surely in or enter into ().
3. On correcting, please cross out with a double line (=) and **initial and date**.

1023259 Real-World Impact of RA

Site number	-	Participant ID
-------------	---	----------------

1. Since you last filled out this questionnaire, did you have any consultations/visits to healthcare professionals for treatment of your rheumatoid arthritis? (Check all that apply)

No visit since you last filled out this questionnaire

Yes → General Practitioner _____ times
(Taiwan: Family Medicine)

Rheumatologist _____ times

Gerontologist _____ times

Orthopedist _____ times

Internist _____ times

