#### 5. STATISTICAL ANALYSIS

##### 5.1 General Considerations

The statistical analysis will be performed using SAS® 9.3 software or a later version (SAS Institute, North Carolina, USA) via SAS Enterprise Guide version 6.1. The statistical results will be displayed using tables, listings and/or graphs for each country. Figures will be performed with SAS®.

Unless otherwise specified, results will be provided as descriptive statistics by country. For categorical measures, data will include the frequency (number of cases [N]) and percentage (%) of total study patients observed in each category. Continuous variables will be described with number of patients with missing observations, mean, standard deviation (SD), median, minimum, and maximum.

The following rules will be followed to define the number of decimal positions to report in study results:

For categorical variables:

- 1 for the percentage.

For most of the continuous variables:

- 1 for the mean, SD, median, minimum, and maximum.
- In continuous variables with low values, 2 decimals for all measures will be reported.

A set of draft table shells (see the document, "AbbVie\_ROCKI\_Tableshell\_V0.2\_2Jan2018.xlsx") will be created in advance to

describe the statistical analysis that will be done to fulfill the objectives of this study. Based on the analysis results the tables will be modified accordingly.

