#### **5.5 Analysis Plan for Additional Secondary Objectives**

- Descriptive statistics will be presented for post-index overall RA related direct healthcare resource utilization (Excel Table 8)

- Consultations/visits to healthcare professionals for treatment of RA (number of patients with  $\geq 1$  visit; categorized by the treatment department listed in 3.5.4)
- Procedures received when visiting the healthcare professional(s) for treatment of RA (number of patients with  $\geq 1$  procedure; categories listed in 3.5.4)
- surgeries received when visiting the healthcare professional(s) for treatment of RA (number of patients with  $\geq 1$  surgery; categories listed in 3.5.4)
- Hospitalizations in relation to RA (number of patients with  $\geq 1$  admission)
- Length of stay in days (mean, SD, median)
- Concomitant medications taken for RA (number of patients with  $\geq 1$  medication; categories listed in 3.5.4))

- Associations between disease severity (measured by DAS28) and PROs (HAQ DI score, SF-36 domain scales, EQ-5D-3L index, WPAI outcomes) will be analyzed using the bivariate linear regression model (Excel Table 9.1). Separate models will be estimated to identify the association between DAS28 and each of the PROs.
- Additionally, in Excel Table 9.2, separate bivariate liner regression models will be estimated to identify the association between change in DAS28 and change in each of the PROs at 12 and 24 weeks after baseline respectively.

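### Post-index resource use is summarised over a fixed 6 months with no allowance for shorter observation, so it is understated, modestly at the planned drop-out.

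*SAP*

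**What the plan says.** **Window and measure.** SAP 3.5 states that "healthcare resource utilization will be summarized over the 6 month post-index period". SAP 5.5 adds that "Descriptive statistics will be presented for post-index overall RA related direct healthcare resource utilization". For consultations, procedures, surgeries, admissions and medications it lists the number of patients with one or more; for length of stay it lists mean, SD and median. Protocol 9.7.6 is no more specific: "Healthcare resource utilization will be described using number and percentage within each category". Neither document gives a rate, an observed-time rule or a denominator specific to HCRU.

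**Denominator.** The general rule in SAP 5.1 for categorical measures is frequency and "percentage (%) of total study patients observed in each category". SAP 3.5.5 says that analysis uses available data and that missing counts are reported for each variable.

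**Follow-up.** Protocol 17.0 lists three kinds of drop-out. The first is "Patient is switched off Adalimumab"; the others are unwillingness to continue and loss of contact. It then says "Once a subject is dropped out from the study, no further information for that subject will be collected". The first two kinds are given the Early Termination Form, whose patient part repeats the HCRU questions (Appendix K); the third is not. Separately, "Patients not completing questionnaires will not be classified as drop-out".

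**Look-back.** The follow-up HCRU form in Appendix J asks: "Since you last filled out this questionnaire, did you have any consultations/visits to healthcare professionals".

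**The concern.** An at-least-one-event share depends on how long each patient is watched. A patient observed for 12 weeks and one observed for 24 enter Table 8 on equal terms, and time that no form covers is treated as time without use. For a given patient, shortening the observation can lower such a share or a count but cannot raise it, so the direction is known.

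The patients affected are:
- those who stop adalimumab or withdraw, observed only to the termination form;
- those lost to contact, observed only to their last form, which may be the baseline one;
- those who return Week 12 but not Week 24, observed for about 12 weeks.

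HCRU is descriptive here, but it is a stated goal of the study (Protocol 4.0), costs are to be assigned from it (Protocol 9.1, SAP 3.1), and the results are meant for payers. The baseline form asks about the previous 6 months. A reader who sets that against partly observed post-index use would see a fall in use that is partly an artefact.

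**Working it through.** **Inputs from the documents.** Drop-out d is 10% with N = 89 (Protocol 9.5) and 13% (SAP 4). The protocol's size reproduces from n = (SD × (z₁₋α + z₁₋β)/Δ)², one-sided: 35.05, rounded up to 36 for HAQ DI, and 39.43, rounded up to 40 for WPAI. Then 40/0.5/0.9 = 88.9, or 89. The documents state no HCRU rate and no timing of drop-out, so there is no HCRU figure to reproduce.

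**Assumptions.** The true 24-week share with at least one event is p; the event rate is constant, λ = −ln(1 − p)/24 per week; all drop-outs are observed for t weeks; drop-outs have the same rate as others unless stated.

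**Reported share with all patients in the denominator:** (1 − d)p + d(1 − e^(−λt)).

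For p = 20% and t = 12, 1 − e^(−12λ) = 1 − √0.8 = 0.1056. Then:
- d = 10%: 0.90 × 20 + 0.10 × 10.56 = 19.06%
- d = 13%: 0.87 × 20 + 0.13 × 10.56 = 18.77%

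| True share | t = 12, d = 10% | t = 12, d = 13% | t = 0, d = 10% | t = 0, d = 13% |
|---|---|---|---|---|
| 5% | 4.75 | 4.68 | 4.5 | 4.35 |
| 20% | 19.06 | 18.77 | 18.0 | 17.4 |
| 50% | 47.93 | 47.31 | 45.0 | 43.5 |
| 90% | 87.84 | 87.19 | 81.0 | 78.3 |

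The t = 0 columns are the upper bound: no form from any drop-out, all still in the denominator. The relative shortfall is then d itself, 10-13%.

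**Mean counts** (if reported or used for costing): observed/true = (1 − d) + d × t/24. At t = 12 this is 0.90 + 0.05 = 0.950 and 0.87 + 0.065 = 0.935, so counts are 5.0% and 6.5% low.

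**Among the drop-outs themselves**, a true 20% would show as 5.4%, 10.6% or 15.4% if they were observed for 6, 12 or 18 weeks.

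**Which denominator matters when.** At t = 0 with equal risk, restricting to patients with a form restores 20%. At t = 12 every drop-out has a form, so the restriction changes nothing and the shortfall stays. The denominator rule therefore deals with patients who have no form; only observed time deals with those partly observed.

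**Patient-time.** With 89 patients and 9 drop-outs at week 12, observed time is 80 × 24 + 9 × 12 = 2028 patient-weeks, against 89 × 24 = 2136 (94.9%). Dividing events by 2028 removes the shortfall if the rate is constant and equal.

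**If drop-outs had twice the rate** (assumed; d = 10%, t = 12), the patient-time rate would be (0.9 × 24 + 0.1 × 2 × 12)λ/(0.9 × 24 + 0.1 × 12) = 24.0λ/22.8 = 1.05λ, against 1.10λ for the full cohort. The rate helps but does not remove informative drop-out.

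**The case against.** The strongest reply is that the SAP never says unobserved time is zero use. SAP 5.1 is a general reporting rule, SAP 5.5 gives no HCRU denominator, SAP 3.5.5 points to available data, and the Table 8 shell is in a separate workbook. This stands in part: a patient with no post-index form may well be treated as missing. It does not help a patient observed for 6 or 12 weeks, who has data and counts as fully observed under either reading.

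The plan also collects more than it might seem to:
- Protocol Table 1 schedules HCRU at early termination, and two of the three drop-out types are given that form.
- A missed Week 12 form alone loses no time, because the Week 24 form looks back to the last completed one. Protocol 9.2.4.7 instead describes a 3-month recall; the two should be reconciled.
- The physician's follow-up form (Appendix C) records surgeries with length of stay, and medications, but not consultations, procedures or non-surgical admissions.

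These points limit the size of the problem and do not remove it.

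A reader might infer a much larger bias by giving every drop-out both no observation and doubled risk: 18.0% reported against 0.90 × 20 + 0.10 × 40 = 22.0%, about a fifth low. The documents do not support that pairing. Progression and adverse events are stop reasons printed on the clinician's termination form, so those patients are planned to return HCRU data. Those with no planned form are the patients lost to contact, and nothing in the documents gives them a higher risk.

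**Conclusion.** The point holds as a modest, downward distortion of a descriptive table. A fixed 6-month window, no collection after drop-out and no use of observed time mean that HCRU for partly observed patients is understated whichever denominator rule is followed.

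At the plan's own 10-13% drop-out, with stops near week 12 and a constant, equal event rate, a true 20% share is about 0.9-1.2 percentage points low. The gap is 0.2-0.3 points at 5% and 2.1-2.7 points at 50%. The 10-13% relative shortfall is a ceiling, not an expectation. As shares approach 100%, as they may for rheumatologist visits, the week-12 effect shrinks towards zero. For length of stay it depends on whether the mean is taken over all patients or only those admitted, which the SAP does not say. Event rates and drop-out timing are assumed throughout.

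A reader might also infer that Table 8 must be split into baseline-Week 12 and Week 12-24. Protocol 9.3 lists HCRU at those times, but the analysis text in 9.7.6 asks for no split. Most items also could not be split for a patient whose Week 24 form covers both intervals.

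**What to change.** In SAP 3.5 and 5.5/Table 8:
1. Use as denominator the patients with at least one post-index HCRU or termination form, and state that this replaces the default in SAP 5.1 for HCRU.
2. Beside the percentages, give a rate per patient-time: total events (the counts already defined in SAP 3.5.4) divided by total time from baseline to the date of the last HCRU or termination form. For concomitant medications a percentage is enough.
3. Show the number of patients observed for less than the full period next to these figures.
4. State that the rate does not remove bias from informative drop-out.

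The cost is SAP wording and a few extra columns in Table 8. No new data are needed, because the HCRU and termination forms are dated and carry explicit boxes for no visit and no hospitalisation, so true zeros can be told from missing forms.
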